Results: Our results showed that Silodosin turned out to be better in expulsing stone as well as in producing lesser side effects and hence better safety profile than Tamsulosin. Silodosin showed greater stone expulsion rate with about 55 patients expulsing stone in less than 14 days in comparison to just about 5 patients on Tamsulosin. Similarly, patients on Silodosin, showed lesser side effects as compared to Tamsulosin. Nine patients on tamsulosin (60.0%) and six patients on silodosin (40.0%) developed orthostatic hypotension. Only a very tiny percentage of patients reported abnormal ejaculation; two individuals on tamsulosin (66.7%) and one patient on silodosin (33.3%). Another side effect that was identified involved headaches, seen by four patients on silodosin (44.4%) and five patients on tamsulosin (55.6%).

INTRODUCTION

Stone disease is one of the most frequent presentations in the field of urology. A large number of these patients arrive with ureteric stones(1). Globally, occurrence of stone formation is 10-12% for men and 6-8% for women. Its prevalence in Pakistan is approximately 16%. The disease's burden has increased in all age categories and both genders over the past 20 years(2). The incidence of urolithiasis in different age groups is 12.2% in the persons 20-29 year old, 29.6% in those who are 30-39-year-old, and 31.5% in 40–49-year-old patients(3).

Medical management ae well as surgical removal are various options available for treating ureteric stones as per American Urology Association (AUA) and European Association of Urology (EAU) guidelines. However, due to risks of surgical approaches there is always an attempt for treatment by using medical expulsive treatment (MET) for ureteric stones first keeping in view different parameters. According to European Association of Urology Guidelines (EAU), the ureteric stones less than 10 mm can be treated with MET(4). Medical expulsive therapy (MET) is a well-established treatment option for distal ureteric stones, despite a sharp increase in minimally invasive techniques(5). Stones smaller than 5 mm have passage rates ranging from 71% to 98%, while stones with size more than 5 mm had expulsion rates ranging from 25% to 53%(6).

Many factors affect stone removal and must be considered while selecting MET for stones like ureteric spasm, location, size, and number of stones and duration for which it is present and also the ureteric architecture etc(7).

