- Bleeding disorders
- Obstruction distal to stone
- Serum Creatinine > 1.3 mg/dl in males and > 1.2 mg/dl in females.
- Congenital renal anomaly/ skeletal malformation
- Previous treatment for the same stone (PCNL/ URS / push back)
- Solitary Kidney
- Prior JJ stent insertion
- Bilateral ureteral stone

DATA COLLECTION AND PROCEDURE:

The protocol will be submitted to Ethical review committee for review and only once the permission is granted, the study will be started. Patients will undergo standard procedure like detailed history taking, examination and routine investigations. Once decided that the patient will undergo MET, the patient will be explained in detail about medications, their potential side effects, follow up and the potential indications for early follow up. Our study will not change any standard process in place except the randomization between Tamsulosin and Silodosin. The data will be kept confidential as a top priority. Only principal investigator and co-principal investigator will have access to the data.

All patients as per inclusion and exclusion criteria as described above will be included in the study. The CT scan (non contrast computed tomography) will be done on (machine parameters at Ganga ram). Only patients with radioopaque stones will be included. Patients falling into the inclusion criteria will be explained about the study and once they agree to participate in study, randomization will be done. Demographic data including patients' age and comorbid, stone-related data including size, location, laterality and number of stones and duration of symptoms will be recorded. The patient will be given either Capsule Tamsulosin 0.4 mg once daily at night or Tablet Silodosin 8 mg once daily at night based on the group assigned. The patient will also be explained about the reasons for follow up earlier than four weeks including fever, persistent pain or gross hematuria. The patients will be called for follow up at 4 weeks with an X-ray KUB without bowel preparation. We will note if the stone has passed or not.

ETHICAL CONSIDERATION:

The funds for supporting this research will be provided by department of pharmacology and therapeutic FJMU, Lahore. Informed consent will be taken from patients prior to research.

DATA ANALYSIS PROCEDURE:

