Data will be entered and analyzed on SPSS version 22. Percentages and frequencies will be calculated for the demographic variables of the patients. The comparison of the two groups will be made by using T- test. P-value of less than 0.05 will be considered significant and the power used will be 0.80.

RESULTS

Frequency and percentage of demographic data

Variables		Frequency	Percentage	
Gender	Male	105	58.7	
	Female	74	41.3	
Income	Less than	108	60.3	
status	50000			
	50000 -150000	69	38.5	
	Greater than	2	1.1	
	150000			
	Normal	166	92.7	
BMI	Obese	13	7.3	
	None	136	76.0	
Comorbidity	HTN	33	18.4	
	Diabetes	10	5.6	

This information sheds light on the sample population's health and demographic distribution, showing a preponderance of people with normal BMIs and lower income levels, as well as a significant percentage of people without comorbid diseases.

In our study there are total 179 patients out of which 74 are females (41.3%) and 105 males (58.7%).

The income, 108 people, or 60.3% of the total, make less than 50,000Rs in month. Just 2 members, or 1.1 percent, make more than 150,000 monthly, while 69 participants (38.5%) have monthly salaries between 50,000 and 150,000.

13 persons (7.3%) are classed as obese, while 166 people (92.7%) have a normal BMI. These numbers represent a sizable fraction of the sample. In terms of comorbidities, 136 individuals (76.0%) state they have no comorbid conditions. Of the people with comorbidities, 10 (5.6%) had diabetes, and 33 (18.4%) had hypertension (HTN).

[figure not shown]

Figure 1: Pie chart of patients using Silodosin and Tamsulosin (Medicine Advised)

Use of medicine (Figure 1)

Tamsulosin and Silodosin, the two drugs prescribed to a group of patients, are distributed as shown in the pie chart. Of the patients, 43% were advised to take Tamsulosin, which is shown as the blue section on the chart. And (57%) of the patients were advised to take silodosin, as shown by the red segment.

Table2: Patient demographic characteristics and study variables are

Varibales	Tamsulosin	Silodosin	p-value	
Body Mass index	Normal	72(43.4%)	94(56.6%)	0.730
	obese	5 (38.5%)	08(61.5%)	
Laterality	Right	65(55.6%)	52(44.4%)	0.001
	Left	12(19.4%)	50(80.6%)	
Symp To CT	Less than 1 week	67(64.4%)	37(35.6%)	
	More than 1 week	10(15.2%)	56(84.8%)	0.001
	More than 2 week	0 (0.0%)	09(100%)	
Posl n Ureler	Proximal	28(51.9%)	26(48.1%)	

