	Mid	08(17.4%)	38(82.6%)	0.001
	Distal	41(51.9%)	38(48.1%)	
Water intake	Less than 1 litre	59(54.6%)	49(45.4%)	
	More than 1 litre	18(25.4%)	53(74.6%)	0.001
Analgesic requirement	Yes	26(61.9%)	16(38.1%)	0.005
	No	51(37.2%)	86(62.8%)	
Time for removal	Less than 14 days	6(10.3%)	52(89.7%)	
	14-21	14(27.5%)	37(72.5%)	0.001
	22-28	57(81.4%)	13(18.6%)	

presented as frequency and percentage with association

The table compares several factors along with the corresponding p-values to assess statistical significance between two drugs tamsulosin and silodosin.

First, based on Body Mass Index (BMI), 43.4% of those with a normal BMI were prescribed Tamsulosin, while 56.6% were recommended Silodosin. On the other hand, among those who were obese, 38.5% were given Tamsulosin and 61.5% were given Silodosin; p-value came out to be 0.730, which meant that there was no statistically significant variation in the medication preferences according to BMI.

15.2% of patients who had pain for more than a week prior to CT scan, received Tamsulosin while 84.8% received silodosin.

51.9% of the patients with proximal ureteric stone were given Tamsulosin and 48.1% received Silodosin.

82.6 percent of patients with mid-ureteric stone problems received Silodosin, while 17.4% received Tamsulosin.

51.9% of patients with distal ureteric stones received Tamsulosin and 48.1% on Silodosin.

Only 38.1% of patients on Silodosin required analgesics, whereas 61.9% of patients on Tamsulosin used analgesics.

89.7% of patients on silodosin had their stone removed in less than 14 days, while only 10.3% of the patients on Tamsulosin had their stone removed in aforementioned duration.

72.5% of patients on Silodosin had their stone removed in 14-21 days, while only 27.5% of the patients on Tamsulosin had their stone removed in same duration.

Moreover, 81.4% on Tamsulosin had their stone removed in 22-28 days and 18.6% patients on Silodosin had it removed in same duration.

		Tamsulosin	Silodosin	p- value
Side	None	61 (40.1%)	91(59.9%)	
effect	Othostatic	09 (60.0%)	06(40.0%)	
	hypotension			0.3.15
	Abnormal	2(66.7%)	1(33.3%)	
	ejaculation			
	Headache	5(55.6%)	4 (44.4%)	

Table 2 Association between Tamsulosin and Silodosin with side effects

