This bar chart presents a comparative examination of the rates of stone expulsion for patients who were suggested to take Tamsulosin or Silodosin during three distinct time periods—less than 14 days, 14–21 days, and 21–28 days.

The results are color-coded, with red bars denoting silodosin and blue bars denoting tamsulosin.

Silodosin shows a markedly greater efficacy in stone expulsion, with about 55 patients expulsing stone in less than 14 days in comparison to just about 5 patients on Tamsulosin.

This suggests that Silodosin is far more successful at facilitating stone removal in less time than Tamsulosin.

While in 14–21days duration, Silodosin continues to work better than Tamsulosin in removing stones. About 20 patients on Tamsulosin were able to successfully remove stone, compared to about 30 people on Silodosin. This implies that while tamsulosin is also beneficial, silodosin retains greater efficacy.

In the span of 21–28 days, 57 patients on Tamsulosin while 13 on Silodosin were able to eliminate stones. In general, Silodosin is quite successful for rapid stone ejection during the first two weeks. Using the intended period for stone

ejection to guide medicine selection, this time-dependent efficacy analysis offers clinicians important information.

[figure not shown]

Figure 3 Survival function

This statistical method is commonly used to estimate the time until an event occurs and to compare the survival curves of different groups. In this case, Kaplan–Meier analysis was performed to assess the duration that patients required to expel kidney stones while receiving either silodosin or tamsulosin treatment. The rate of the expulsion of stone and the time for it, for both groups, was evaluated using this method, as can be seen in Figure 2.

The log-rank test was applied to compare the rate and time for stone expulsion between the two groups. It is a hypothesis test for comparing the survival distributions of two samples. It was used in this study to see if patients treated with silodosin and those treated with tamsulosin had significantly different times for stones to be expelled. With a p-value of 0.05, the log-rank test findings showed that there was statistically significant difference between the two groups. This indicates that both groups' times to stone expulsion were statistically comparable.

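### The only planned between-arm analysis is an unadjusted t-test; the Results leave it without saying so and adjust no efficacy comparison, although stone location and symptom duration differ greatly by arm

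*Combined protocol and SAP*

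**What the plan says.** **Plan.** The Data Analysis Procedure gives the software, descriptive percentages, a 0.05 threshold, a power of 0.80 and one comparison: "The comparison of the two groups will be made by using T- test". The Operational Definitions make efficacy binary: no stone on X-ray KUB at 4 weeks.

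**Prognostic factors.** The Introduction says many factors affect stone removal, "like ureteric spasm, location, size, and number of stones and duration for which it is present". Under Data Collection and Procedure, "stone-related data including size, location, laterality and number of stones and duration of symptoms will be recorded". No analysis use is given for them. The only scheduled visit is at the end: "The patients will be called for follow up at 4 weeks with an X-ray KUB without bowel preparation".

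**Results.** "In our study there are total 179 patients", it says. On the balance of the arms it reports that "15.2% of patients who had pain for more than a week prior to CT scan, received Tamsulosin while 84.8% received silodosin" and that "82.6 percent of patients with mid-ureteric stone problems received Silodosin, while 17.4% received Tamsulosin". For efficacy, "The log-rank test was applied to compare the rate and time for stone expulsion between the two groups", alongside Kaplan-Meier curves. Nothing says that these methods replace the t-test, and no t-test result is identified. The survival text then calls the same log-rank result significant, says the two arms' times were comparable, and finally says significance was not reached. The Conclusion states without qualification that silodosin is the more successful drug.

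**The concern.** For a binary clearance outcome, a t-test and a test of proportions differ little. A t-test does not suit nominal side-effect categories or three removal-time bands, and the plan offers nothing else. The reader cannot tell which analyses were intended beforehand.

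The larger matter is comparability. The characteristics table prints row percentages, which hide how different the arms are. Once these are turned into percentages of each arm, two factors that the document itself calls relevant to stone removal are far out of balance. Stone size, the third, is not shown by arm. An unadjusted efficacy difference then mixes the drug effect with the case mix. The direction is not known either: silodosin has more patients with longer symptoms, so its crude advantage is inflated if such patients expel more often and understated if they expel less often.

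**Working it through.** **1. The plan's own figure.** The Sample Size section gives 208. With 64% v 83% (difference 19 points), two-sided 0.05 (sidedness assumed) and power 0.80, the two-proportion formula gives

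n = [1.96√(2 × 0.735 × 0.265) + 0.842√(0.64 × 0.36 + 0.83 × 0.17)]² / 0.19² ≈ 83.5.

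The continuity correction raises this to 94; 94 × 1.10 = 103.4, so 104 per arm and 208 in total. The sizing therefore assumed a comparison of proportions.

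**2. Which test the tables use.** Pearson chi-square from the printed counts:

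| Row | Chi-square (df) | p | Printed p | t-test on category codes, p |
|---|---|---|---|---|
| Side effects (61/9/2/5 v 91/6/1/4) | 3.54 (3) | 0.315 | 0.315 | 0.065 to 0.129 over the six orders with 'none' lowest |
| Location (28/8/41 v 26/38/38) | 16.59 (2) | 0.00025 | 0.001 | 0.69 in anatomical order |
| Analgesics (26/51 v 16/86) | 7.99 (1) | 0.0047 | 0.005 | 0.0045 |
| BMI (72/5 v 94/8) | 0.12 (1) | 0.730 | 0.730 | 0.732 |

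The two-level rows cannot tell the tests apart; side effects can.

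**3. Imbalance by arm (tamsulosin 77, silodosin 102).**
- Symptoms to CT under 1 week: 67/77 = 87.0% v 37/102 = 36.3%; three-level chi-square 47.14, 2 df, p = 5.8e-11.
- Mid-ureter: 8/77 = 10.4% v 38/102 = 37.3%; location p = 2.5e-4.

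**4. Crude expulsion.**
- Before day 14: 6/77 = 7.8% v 52/102 = 51.0%, difference 43.2 points.
- By day 21: 20/77 = 26.0% v 89/102 = 87.3%, difference 61.3 points.

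**5. What adjustment could do.** Outcome is not tabulated by location, duration or size, so no adjusted estimate can be computed. Bounds come from every allocation of each arm's expulsions to strata that fits the printed margins, using the Mantel-Haenszel risk difference Σw(p_S − p_T)/Σw with w = n_T·n_S/(n_T + n_S).

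Example, duration (67/10 v 37/65), before day 14: w = 67 × 37/104 = 23.84 and 10 × 65/75 = 8.67. The lowest value puts all early expulsions in the longer-symptom stratum, where the difference is 52/65 − 6/10 = 0.20: 8.67 × 0.20/32.50 = 0.053.

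| Adjusted for | Before day 14 (points) | By day 21 (points) |
|---|---|---|
| Duration alone | 5.3 to 72.9 | 36.6 to 72.8 |
| Location alone | 22.4 to 60.5 | 51.9 to 70.2 |

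The first row merges the two longer duration bands. Keeping all three gives 4.4 to 74.2 and 36.8 to 76.1. Joint adjustment, and adjustment for size, cannot be bounded.

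**6. Log-rank from the printed bands, silodosin arm.**
- Expected: 58 × 102/179 = 33.05; 51 × 50/121 = 21.07; 70 × 13/70 = 13.00; total 67.12.
- Observed 102; variance 9.66 + 7.21 + 0 = 16.88.
- Chi-square = (102 − 67.12)²/16.88 = 72.1, p = 2e-17.

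**7. Four-week clearance.** Removal times sum to 6 + 14 + 57 = 77 and 52 + 37 + 13 = 102, so all 179 analysed patients are shown as clear by day 28. Any difference lies among unanalysed patients, whose numbers conflict. The Abstract has 208 − 16 − 12 = 180 remaining, but its arms sum to 89 + 93 = 182. The table has 102 silodosin patients, more than the 93 said to remain.

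| Account | Unanalysed (T v S) | All unanalysed counted as failures | Worst to best case for silodosin |
|---|---|---|---|
| Table: 77/104 v 102/104 | 27 v 2 | 24.0 points (95% CI 15.2 to 32.9) | −1.9 to 26.0 |
| Abstract: 89/104 v 93/104, assuming all 89 and 93 cleared | 15 v 11 | 3.8 points (−5.1 to 12.8) | −10.6 to 14.4 |

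**The case against.** **Randomisation makes adjustment optional.** In a sound randomised trial an unadjusted comparison is valid, so omitting covariates is not in itself an error. That is right in general. But an imbalance with p = 6e-11 is not plausible chance; it points to allocation, attrition or data problems that a model cannot mend. This stands, and it is why the remedy starts with patient counts and ends with a qualified conclusion.

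**No reversal is shown.** Every single-factor bound stays positive. This also stands: the finding concerns validity and effect size, and does not show that the result is wrong.

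**The test identification depends on coding.** With mid-ureter coded at either end, the location t-test gives p = 0.0004 or 0.0007, compatible with the printed 0.001. The anatomical order used here is the table's row order but remains an assumption. Side effects carry the inference: no ordering of equally spaced codes gives 0.315 (nearest 0.257 and 0.337).

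**The clearance scenarios are rough.** The Abstract attributes 16 exclusions to the study ending early, and those patients are not evidently failures. The accounts imply 29 and 26 unanalysed patients, against 28 stated. The figures are scenarios, and their intervals do not cover the uncertainty in the counts.

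**The printed log-rank p of 0.05 may restate the threshold.** Possibly. The three incompatible readings of the result remain either way.

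**Conclusion.** The concern holds and should be fixed. The plan has a single unadjusted t-test, the Results use other methods without declaring the change, and no efficacy comparison takes account of the large differences in symptom duration (87.0% v 36.3% under one week) and location (10.4% v 37.3% mid-ureter).

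On the printed margins, neither factor alone removes silodosin's early advantage, but duration alone leaves its size before day 14 open from about 5 to 73 points. The joint effect of the factors and the effect of stone size are unknown, as is the direction of bias. Evidence on 4-week clearance ranges from a clear difference to none, depending on which set of arm counts is believed; the documents give no ground for preferring either.

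These results rest on the printed counts, with all 179 removal times treated as expulsions in the stated bands. The unqualified efficacy statement in the Conclusion is not supported as written.

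**What to change.** Leave the t-test sentence as the record of the plan and add the following, labelled post hoc.

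1. **Counts and clearance.** Reconcile 104/104, 89/93 and 77/102, and state the status of every randomised patient by arm. Report the 4-week clearance risk difference with a 95% confidence interval and best/worst-case bounds, under each account until they are reconciled. With no printed failures, a clearance model cannot be fitted.
2. **Time to expulsion.** Report it crude and adjusted for stone size (mm), location and symptom duration (under 1 week v 1 week or more), main effects only, in a grouped-time or ordinal model on the three bands. Use Cox regression only if expulsion dates exist, since only a 4-week visit is scheduled. Do not cross-stratify: if location and duration are independent within arm, tamsulosin would have about 8 × 10/77 = 1.0 patient who is both mid-ureteric and symptomatic for a week or more.
3. **Side effects.** Use chi-square or, with three of eight expected counts below 5 (1.3, 1.7 and 3.9), Fisher's exact test (p = 0.32).
4. **Reporting.** Show stone size by arm, declare the departure from the t-test, re-run the log-rank test, reconcile the three statements about it, and qualify the Conclusion, because adjustment cannot repair an allocation or attrition failure.

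**Cost.** Re-analysis of data the plan says are recorded, plus a few lines of text. Item 1 needs patient status by arm, which the documents do not give. The adjusted result is post hoc and its interval may be wider. In 1000 simulated data sets at the printed margins, the standard error of the log hazard ratio rose from 0.254 to 0.286, about an eighth. That simulation assumed location and duration independent within arm and no covariate effect, and left out stone size, so the real cost may be higher.
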